12.0 SELECTION OF SUBJECTS

12.1 Study Population

This study will enroll approximately 40 subjects diagnosed with COVID-19 who are at risk for developing acute respiratory distress syndrome (ARDS) receiving standard of care including anticoagulation. Randomization of subjects will be stratified by use of IL-6 antibody therapy.

Subjects who do not meet all of the inclusion criteria or who meet any of the exclusion criteria are not eligible to participate in the study.

12.2 Inclusion Criteria

1. Written or verbal informed consent by subject or subject representative is obtained
2. Male or female subjects age 18 to 80 years, inclusive
3. SARS-CoV-2 infection confirmed with WHO criteria (including a positive PCR of any specimen, e.g., blood, respiratory, stool, urine, or any other body fluid)
4. Chest imaging (radiograph, CT scan or lung ultrasound) with abnormalities consistent with COVID-19 pneumonia
5. SpO₂ ≤ 92% on room air (RA), RR ≥ 24 breaths per min on RA, and/or requirement for supplemental oxygen
6. At least 1 risk factor which may put patient at higher risk for more severe illness from COVID-19: Age > 65, underlying serious heart disease, chronic lung disease, moderate to severe asthma, body mass index of ≥ 40 or diabetes
7. C-reactive protein > 35 mg/L
8. No known allergies to the study drug or its excipients

12.3 Exclusion Criteria

1. Suspected active bacterial, fungal, viral, or other cause of respiratory failure other than COVID-19
2. Known or suspected immunosuppression with immunosuppressant medications or chemotherapeutic agents
3. Active primary lung cancer or another metastatic malignancy to the lungs
4. Moderate to severe liver failure (see [section 12.4](#)) defined by Child-Pugh score of ≥ 7 measured by:
 - Total bilirubin
 - Serum albumin
 - INR
 - Ascites
 - Hepatic encephalopathy
5. The following abnormal laboratory tests if any of the criteria are met:
 - a. Platelet Count < 75,000 /mm³
 - b. White Blood Count < 2500 /mm³
 - c. ALT or AST or Total Bilirubin > 3 x ULN
 - d. Bilirubin > 3 mg/dL
 - e. Serum albumin less than 28 g/L
6. Subject is on dialysis
7. On home ventilator support or continuous domiciliary O₂ therapy for baseline lung disease
8. Active tuberculosis (TB) infection
9. Lactating or pregnant at Screening

10. History of stomach or intestinal surgery or any other condition that could interfere with or is judged by the Investigator to interfere with absorption, distribution, metabolism, or excretion of study drug
11. Treatment with an investigational drug or off-label medication within 5 half-lives or 30 days whichever is longer prior to study drug treatment
12. Participating in another COVID-19 clinical trial
13. Any other serious medical condition or abnormality that, in the Investigator's opinion, would preclude participation in the study.

12.4 Child-Pugh Scoring Table

Subjects will be excluded from study if Child-Pugh score at screening is ≥ 7 .

Table 2 Child-Pugh Scoring Table

Measure	1 point	2 points	3 points
Bilirubin (total) mg/dL	<2	2-3	>3
Serum albumin g/L	>35	28-35	<28
INR	<1.7	1.71-2.20	>2.20
Ascites	None	Mild	Severe
Hepatic encephalopathy	None	Grade I-II (or suppressed with medication)	Grade III-IV (or refractory)

12.5 Screen Failures

A Screen failure is defined as a potential subject who did not meet one or more criteria required for participation who consent to participate in the clinical trial but is not subsequently randomly assigned to the study intervention or entered in the study.

Individuals who do not meet the criteria for participation in this trial (screen failure) due to abnormal clinical laboratory results may be rescreened. Study staff should notify sponsor prior to rescreening.

12.6 Subject Withdrawal/Discontinuation Criteria

A subject may request to be withdrawn from the study at any time for any reason.

The Investigator may interrupt the treatment of any subject whose health or well-being may be compromised by continuing participation in the study. The following instances require subjects to be withdrawn from the study:

- Subject fails to adequately comply with the dosing, evaluations, or other requirements of the study at the discretion of Investigator
- Subjects who have adverse events that require discontinuation of study medication
- Subjects who, in the opinion of the Investigator, should be discontinued for their well-being

- Subjects who are no longer able to understand task instructions or to perform tests adequately
- Subject becomes pregnant during the study. See [Section 18](#) for reporting requirements and follow-up of the pregnancy

If a subject withdraws or is removed from the study for any reason, the reason and date of discontinuation of study medication should be recorded in the appropriate section of the Case Report Form (CRF). At the time of study discontinuation, every effort should be made to ensure that the scheduled study procedures and evaluations for that day are performed. Subjects who are discontinued from study drug for reasons other than loss to follow-up or withdrawal of consent will remain in the study and continue regularly scheduled efficacy and safety assessments.

The study sponsor reserves the right to discontinue the study at any time for medical or administrative reasons.

12.7 Subject Stopping Criteria

A subject should be withdrawn from the study if any of the following abnormal lab values occur, **after repeat testing**:

- AST or ALT or total bilirubin $>3 \times$ upper limit of normal (ULN)
- Bilirubin $>3 \text{ mg/dL}$
- Serum albumin less than 28 g/L
- White blood count $<2500/\text{mm}^3$
- Platelet count $<75,000/\text{mm}^3$

A subject should also be withdrawn from the study if any of the following adverse events occur:

- Nausea considered moderate or severe and related to study drug by investigator for greater than 3 consecutive days despite maximal supportive therapy
- Vomiting considered moderate or severe and related to study drug by investigator for greater than 3 consecutive days despite maximal supportive therapy
- Diarrhea considered moderate or severe and related to study drug by investigator for greater than 3 consecutive days despite maximal supportive therapy
- Occurrence of an SAE or grade 3 adverse event related to study drug

Subjects who are withdrawn/discontinued from study drug to an abnormal lab result or adverse event will remain in the study and continue regularly scheduled efficacy and safety assessments.

12.8 Study Stopping Criteria

An independent medical safety monitor will evaluate safety on an ongoing basis during the study. After each of the first three subjects are dosed, the medical safety monitor will review the data with the PI and sponsor and will make a recommendation to proceed/stop. After the first three subjects are evaluated, the medical safety monitor will continue to review safety data throughout the study.

If two or more subjects experience similar adverse events of moderate or severe intensity or similar serious adverse events related to study drug or if two or more subjects discontinue study treatment due to safety concerns, study dosing will be temporarily halted until the safety data has been reviewed. Once reviewed by an independent safety monitor, sponsor and PI, a determination will be made to continue or stop the study.

13.0 TREATMENTS

MN-166 (ibudilast) will be administered as MN-166 50 mg (5 capsules) b.i.d for 7 days. Study drug may be taken with food or within an hour of eating to improve gastrointestinal tolerability. Subjects who cannot tolerate a b.i.d. dosing regimen may be administered a t.i.d. dosing regimen (40 mg at breakfast, 30 mg at lunch, 30 mg dinner). Subjects who cannot tolerate this regimen will be discontinued from the study.

Day 1 study drug may be administered starting with the PM dose. If the first dose of study drug is administered in the PM then the last dose should be administered on Study Day 8 in the AM.

Matching placebo will also be provided and will be administered as 50 mg (5 capsules) b.i.d. for 7 days.

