10.1 Primary Efficacy Variable Analysis

The co-primary efficacy endpoints are listed below. The primary analysis for each of these two endpoints will be conducted using Pearson's chi-square tests. Because study success is defined as success on both, each of the two co-primary endpoints will be tested using a one-sided significance level of 0.025.

- Proportion of subjects free from respiratory failure
 - Calculate the proportion of the subjects free from supplemental oxygen (invasive mechanical ventilation, non-invasive ventilation, high-flow oxygen, ECMO, CPAP, BiPAP, nasal cannula) at Day 7
- Proportion of subjects with improvement in clinical status using the NIAID 8-point ordinal scale and discharge record at Day 7
 - Calculate the proportion of the subjects who improved at least one-point from baseline

For each of the two co-primary endpoints, subjects whose response status is unknown will be assumed to be nonresponders.

A supportive analysis for each of the two co-primary endpoints will be conducted using the Mantel-Haenszel test stratified by the randomization stratification variable (use of IL-6 antibody therapy).

Confidential

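### The protocol gives conflicting instructions on whether a subject who stops study drug also leaves the study; where the exit wording is followed, Day 7 outcomes may be imputed as failures instead of observed.

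*Combined protocol and SAP*

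**What the plan says.** Three parts of the protocol take the subject out of the study:

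- Section 13.0, on subjects who cannot tolerate the alternative regimen: "Subjects who cannot tolerate this regimen will be discontinued from the study". The section does not mention later assessments.
- Section 12.6, opening its list: "The following instances require subjects to be withdrawn from the study". One listed instance is "Subjects who have adverse events that require discontinuation of study medication".
- Section 12.7, on laboratory values: "A subject should be withdrawn from the study if any of the following abnormal lab values occur". On adverse events: "A subject should also be withdrawn from the study if any of the following adverse events occur".

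Three parts keep the subject in:

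- Section 12.6, near its end: "Subjects who are discontinued from study drug for reasons other than loss to follow-up or withdrawal of consent will remain in the study", with efficacy and safety assessments continuing on schedule.
- Section 12.7, at its end: "Subjects who are withdrawn/discontinued from study drug to an abnormal lab result or adverse event will remain in the study", again with scheduled assessments.
- Section 13.5: subjects with confirmed abnormal values, on the same laboratory limits as 12.7, stop medication but continue the scheduled tests and assessments.

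SAP section 6 defines the full analysis set as all randomised subjects. For both Day 7 co-primary endpoints, SAP 10.1 states that "subjects whose response status is unknown will be assumed to be nonresponders".

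**The concern.** Stopping drug and leaving the study have different consequences for the data. A subject off drug who stays in still supplies oxygen status, NIAID score and survival. A subject who has left may supply none of these. Because the protocol describes the same subjects both ways, whether an outcome is observed or imputed can depend on which sentence a site acts on.

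Two things are at stake. First, nonresponder imputation may be applied to subjects whose Day 7 status could have been recorded. Second, protocol sections 16.0 and 16.5 run adverse event collection until the subject discontinues or completes, so study exit also closes the safety record and may end survival follow-up.

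The loss need not be balanced between arms. Protocol section 9.1 reports a dose-related increase in nausea and a slight one in gastrointestinal events and headache. If intolerance takes subjects out of the study, more of them would be expected on MN-166.

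**Working it through.** **Step 1. Set the instructions side by side.**

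| Reason for stopping drug | Text taking the subject out | Text keeping the subject in |
|---|---|---|
| Laboratory limit, confirmed on repeat | 12.7 opening sentence | 12.7 closing sentence; 13.5 |
| Adverse event listed in 12.7 | 12.7 second list; 12.6 list | 12.7 and 12.6 closing sentences |
| Other adverse event requiring drug to stop | 12.6 list | 12.6 and 12.7 closing sentences |
| Cannot tolerate the alternative regimen | 13.0 | None in 13.0; 12.6 or 12.7 only if read across |

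The first three rows conflict within a section or between neighbouring ones. The fourth is the least protected. The 12.6 closing sentence speaks of subjects discontinued from study drug, whereas 13.0 discontinues them from the study.

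**Step 2. Follow an exit through the analysis.** Section 12.6 asks for that day's procedures at discontinuation. SAP 7.3 allows a window of 0 days for Days 2 to 7, and the SAP has no rule carrying an earlier value to Day 7. A subject who leaves before Day 7 therefore has unknown status unless the discharge record supplies it, and SAP 10.1 makes that nonresponse. The rule is written only for the two co-primaries; the SAP states no missing-data rule for the secondary proportions.

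**Step 3. Sensitivity to one subject.** The plan has no power or effect-size figure to reproduce. Inputs from the documents are about 40 subjects (SAP 5), 1:1 allocation (SAP 3.3), hence 20 per arm, Pearson's chi-square (SAP 10.1) and one-sided alpha 0.025 (SAP 7.5). The response counts are assumptions.

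With a and b responders of n per arm and pooled rate p̄ = (a+b)/(2n), z = (a/n − b/n) / √[p̄(1 − p̄)(2/n)].

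- 15/20 vs 8/20: p̄ = 0.575, z = 0.35/√(0.575 × 0.425 × 0.1) = 2.24, one-sided p = 0.013.
- 14/20 vs 8/20: p̄ = 0.55, z = 0.30/√(0.55 × 0.45 × 0.1) = 1.91, p = 0.028.
- 16/20 vs 10/20: p = 0.023. With 15/20 vs 10/20: p = 0.051.

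In each pair, rescoring one MN-166 responder as a failure moves the result across 0.025. One subject is 1/20 = 5 points of the arm's rate.

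**Step 4. Range over assumed losses.** Let d be the share of the MN-166 arm whose Day 7 status is lost, independently of response, with no placebo loss. The observed MN-166 rate becomes p(1 − d), so the difference shrinks by p × d. Exact binomial power for one endpoint at 20 per arm:

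| Assumed true rates | d = 0 | 5% | 10% | 15% | 20% |
|---|---|---|---|---|---|
| 80% vs 40% | 75% | 64% | 52% | 41% | 31% |
| 80% vs 50% | 53% | 40% | 29% | 20% | 13% |

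For 80% vs 40%, the observed difference falls from 40 to 36, 32, 28 and 24 points.

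**Step 5. Direction.** With equal true rates of 50%, losing 10% of the MN-166 arm lowers the exact one-sided rejection rate from 2.1% to 1.0%. Under these assumptions the loss works against the drug.

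**The case against.** The best defence is that this is loose terminology and that the passages dealing with data collection all agree. The closing sentence of 12.6 is general, excepting only loss to follow-up and withdrawal of consent, and intolerance is neither. Section 12.7 repeats the retention rule for adverse events and laboratory values, and 13.5 repeats it for laboratory values. Section 13.0 is a dosing section and does not tell sites to stop assessments. The exposure is also narrow: 13.0 applies only after both regimens have failed within a 7-day course, NIAID and oxygen status are scheduled daily, and the NIAID co-primary also draws on the discharge record. Finally, scoring intolerance as nonresponse can be a deliberate choice.

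Much of this stands. Most of the text favours retention, so a reader might infer that sites necessarily stop collecting outcomes under 13.0, but the documents do not say so. The harm is conditional. A reader might also call any resulting shift bias without qualification; that depends on whether intolerance was meant to count as failure.

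The defence does not remove the conflict. The exit wording is operative text, in one place phrased as a requirement. Elsewhere the plan treats study exit as a real event: SAP 8.1 tabulates early withdrawals, and SAP 11.1 tabulates adverse events leading to study discontinuation. If nonresponse after intolerance was intended, it should be a stated rule applied to every such subject, not a consequence of which sentence a site follows.

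**Conclusion.** The contradiction is real and should be resolved. Its consequence is possible, not certain, and its size cannot be determined: the documents give no intolerance, dropout or response rate for this trial. The calculations show only that, at about 20 per arm, one subject can matter. That the loss would fall more on MN-166 is inferred from section 9.1, which also describes the drug as generally well tolerated.

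Three stronger readings are not supported:

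- **That the all-randomised analysis set is broken.** SAP 6 keeps every randomised subject, and SAP 10.1 keeps them in the denominator of both co-primaries. What may be lost is the observed outcome.
- **That a definite number of points is lost.** One could assume a 65% response and 18 per arm, and compute 0.65 × (18 − k)/18 = 61%, 58% and 54% for k = 1, 2 and 3 lost. The 65% and the k are not in the documents. The 18 is half of the 31 + 5 = 36 subjects consented (SAP 13.1 and 13.2), and consented is not the same as randomised.
- **That the result could falsely favour ibudilast.** Loss weighted to MN-166 works the other way. The risk is of hiding a real signal in a study that SAP 5 says will be used to design future ones.

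**What to change.** Reconcile protocol sections 13.0, 12.6, 12.7 and 13.5 so that one rule governs data collection:

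- Use one term for stopping study drug and a different one for leaving the study.
- State that every randomised subject who has not withdrawn consent continues the scheduled oxygen status, NIAID and survival assessments, by telephone where the protocol allows.
- Make the NIAID score and survival status required items of those calls. Footnote e of Table 1 now lists only oxygen use and levels, adverse events and concomitant medications, and makes other assessments optional.

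This does not touch when or why drug is stopped, which is for the sponsor's clinicians. The cost is a wording amendment and somewhat fuller telephone contacts at visits already scheduled. Day 60 applies only to subjects enrolled under Amendment 4 (SAP 3.1).

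SAP version 2.0 already reports consent counts and describes randomisation in the past tense. If enrolment has ended, an amendment cannot recover data already missed. The sponsor should then identify, by arm, who left under 13.0, 12.6 or 12.7, and retrieve Day 7 and vital status where consent allows. A sensitivity analysis should repeat both co-primary tests with retrieved values and vary the remaining unknowns from all nonresponders to all responders. With a sample of this size, that is a small task.

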13.1 Study Drug Supply

MN-166 and matching placebo will be provided in 10 mg non-vegetarian capsules in polyethylene bottles and will be stored at room temperature.

MN-166 is an extended release pharmaceutical preparation comprised of white extended release granules contained in a No.4 white capsule ([Table 3](#)).

Table 3 Study Drug Information

Investigational Drug	MN-166 or matching placebo
Formulation	10 mg capsules
Frequency	MN-166: 50 mg b.i.d. for 7 days
Storage Conditions	Store at room temperature

13.2 Study Drug Packaging and Labeling

At a minimum, the following information will be included on each package:

- Name of Sponsor
- Study number/Acronym/IND number
- Route of administration
- Quantity of dosage unit
- Directions for use
- Storage conditions
- Space for information to be completed by Investigator/designee:
 - Name and telephone number of Investigator

- Dispensing date
- Subject number
- Statement “Caution: New Drug – Limited by federal law to investigational use”

13.3 Study Drug Storage

The study drug should be stored at room temperature. Do not freeze.

13.4 Study Drug Administration

The study drug will be dispensed by appropriately qualified site study staff.

Investigational clinical supplies will be received by the PI or a designated person at the study site, handled and stored safely and properly, and kept in a secured location to which only the Investigator and/or designated assistants have access. Clinical supplies are to be dispensed only in accordance with the protocol.

Study drug will be administrated orally. If subjects become dependent on a gastric tube, study drug can be given via gastric tube by opening the capsules in an enteral syringe, then suspend in 30 ml distilled water. It is recommended that the gastric tube is rinsed before and after each study drug delivery via gastric tube. Study drug is extended-release granule in gelatin capsule and gelatin capsule has no functionality in the release of drug.

Also, open capsule MN-166 administration has been used in 2 clinical trials in ALS patients who became gastric tube dependent due to bulbar symptoms, with no safety concerns.

13.5 Dose Interruptions

The following abnormal laboratory tests should be repeated within 24 hours if any of the criteria are met:

- AST or ALT or Total Bilirubin $>3 \times$ upper limit of normal (ULN)
- Bilirubin $>3 \text{ mg/dL}$
- Serum albumin less than 28 g/L
- White blood count $<2500/\text{mm}^3$
- Platelet count $<75,000/\text{mm}^3$

If, after repeat testing, the laboratory value is still outside the above-stated limits, then the subject should stop study medication. While dosing is withheld, subjects will continue tests and assessments according to the schedule defined in the protocol (and may also undergo additional assessments to evaluate the laboratory abnormality as per the Investigator’s standard practice).

13.6 Method of Assigning Subjects to Treatment Groups

Subjects will be assigned to treatments based on a randomization scheme generated by a computer program. The randomization scheme will be reviewed and approved by an independent statistician from the Sponsor and locked after approval.

13.7 Blinding

The subject and all study staff members including the Sponsor will be blinded to the treatment codes. Randomization information will be kept strictly confidential, filed securely by an appropriate group at the sponsor company and accessible only to authorized personnel until the time of unblinding.

13.8 Prohibited Medication

The use of any unauthorized investigational therapy is prohibited during the study.

13.9 Treatment Compliance

Records of treatment compliance for each subject will be kept throughout the study. The clinical research monitor will review treatment compliance during site visits and at the completion of the study.

14.0 STUDY PROCEDURES

14.1 Informed Consent

The Principal Investigator or a qualified designee (e.g., a licensed, qualified medical practitioner such as a physician's assistant or a nurse practitioner) listed on FDA Form 1572 will explain the study to the subject or subject's representative, answer all of the subject's questions, and obtain written or verbal informed consent before performing any study-related procedure. Informed Consent should be conducted in accordance with local requirements. Subject should be able to verbally describe the benefits and risks associated with this study and what other treatment alternatives are available (as described in the Informed Consent form).

Only subject or subject's representative who provide informed consent, as assessed and documented by the Investigator, will be enrolled. The subject is required to provide written informed consent prior to undergoing any study procedures. If subject is unable to sign their full name, an "X" can be acceptable. A copy of the signed and dated informed consent (in a language in which the subject is fluent) is required to be given to the subject. If a subject withdraws consent, data collected up to the time of discontinuation will be used to evaluate study results.

